14.3 Informed Consent Process

2
3 Consent will be obtained by CITI certified employees of PRISMA with experience in
4 biomedical research and community based research. Both parents must sign the
5 consent form for children of this age to participate in clinical trials in Peru. The
6 discussion will begin in a public forum where interested parties are invited by public
7 loudspeaker to a community center. Individuals who retain interest in having their
8 children participate after this forum will be invited to the study center where the process
9 will be repeated in a private setting.

10
11 The study involves young children. To ensure the parental permission to have the child
12 participate is valid, the study will be explained in detail to ensure that parents understand
13 the risks and benefits for their particular child. The study team has extensive experience
14 working with young children and their parents and the stress of study participation to the
15 child participants will be minimized in part by clinical rapport gained from this experience.

16
17 A standard signed consent document will be used. Children of guardians lacking
18 signatory capacity will not be allowed to participate. Study participants will be given a
19 copy of the consent document to ensure their understanding (by giving them
20 opportunities to present and discuss with 3rd parties, and to provide necessary contact
21 information with study personnel or local or international IRBs overseeing the study.

14.3.1 Informed Consent/Accent Process (in Case of a Minor)

23
24 All subjects are under the age of 2 years and will participate with parental permission.

14.4 Exclusion of Women, Minorities, and Children (Special Populations)

25
26 Not relevant.

14.5 Subject Confidentiality

27
28 The confidentiality of research subjects is strictly maintained by the study team.
29 Although the study monitors and agencies may access study information in the oversight
30 of the clinical trial to ensure quality measures are being met or that human subjects are
31 being treated appropriately. Data regarding subjects will not be released to other third
32 parties.

33
34 The prolonged storage of source documents with identifiers is done at a secure space
35 with limited access and rigorous security. Digital records of the study and nearly all
36 source documents are identified by PID only to diminish risk of the dissemination of
37 information regarding the identity or characteristics of subjects.

1
2 Databases lack identifiers and are further protected by password. All study personnel,
3 including data entry personnel, receive specific training on their obligations regarding the
4 privacy of participants and their families.

5
6 **14.6 Study Discontinuation**

7
8 In the case that the study is discontinued based on safety concerns, follow-up will be
9 maintained to document all relevant safety outcomes.

10
11 **14.7 Future Use of Stored Specimens**

12
13
14 Data collected will be stored in servers at AB PRISMA and Johns Hopkins University
15 Bloomberg School of Public Health. Specimens will be stored at the laboratories of AB
16 PRIMSA in Iquitos Peru, with the option of secure storage at Johns Hopkins University. In
17 the parental permission form, there is a provision for the use of residual sample for long
18 term use for research related to the discovery and evaluation of new tests for enteric
19 infections, microbiome research, testing for biomarkers of undernutrition, and
20 gastrointestinal function. Subjects can withdraw their consent to have their samples in
21 this biorepository and still participate in the study. Subjects may withdraw their consent to
22 have their samples stored at a date no later than 2 years after the completion of the study.
23 De- identified samples will be shared with third parties only under a materials and transfer
24 agreement assuring compliance with restriction (No human DNA analysis, not for profit,
25 not to be used to derive patents) are upheld.

26

1

2

3 **15 DATA HANDLING AND RECORD KEEPING**

4

5 Data collected in paper format will be transferred to a data unit at the research center
6 and entered into a data management system. Records will be checked by a study
7 physician or coordinator prior to being transferred for data entry.

8

9 Personal identifiers (such as names, birthdates, addresses) will be collected and held
10 on a small number of forms that will not be entered into the electronic database.

11 All data from the study will be held in secure space locally to permit validation of the
12 electronic database by auditors (including the Medical monitors, study PIs, INS staff, or
13 other trial auditors from or designated by NIDDK).

14

15

16 **15.1 Data Management Responsibilities**

17

18 All study data must be held in secure areas with limited access. Transfer of physical
19 files and electronic data will be kept to a minimum. Transfer of files and backup files
20 will all be done on password protected files. Transfer of study files will always be done
21 by a study team member. The site data manager has responsibility for the security and
22 integrity of the physical files, the existence and safety of back up files, and the
23 protection of digitally stored information. Data is held on a server in Iquitos Peru with a
24 mirror copy at Johns Hopkins in Baltimore Maryland.

25

26 All records and laboratory reports must be reviewed by the study physician, PI, study
27 coordinator or designee before being transferred to the data unit. All corrections made
28 on CRFs will be made by striking thru the original text with a single line and by writing
29 the correct data above, beside or below the original entry. The correction must be
30 accompanied by the initials of the individual making the change and the date of the
31 change. The original entry must not be obscured.

32

33 If the form is stamped as being already entered in the electronic database, it is the
34 responsibility of the individual initialing the change on the paper form to contact the data
35 center to ensure entry of the change in the study database.

36

37 The data management team in Iquitos will ensure records from participants are
38 adequate and complete. They will discuss active issues regarding incomplete or data
39 that appears to have unexpected values with the Study Coordinator to minimize
40 recurrence.

15.2 Data Capture Methods

2
3 Data captured on case report forms will be documented on paper forms. Clinical
4 laboratory data will be entered directly from the source document. These forms will
5 be entered into the study base on an ongoing basis. Once forms are entered, the
6 forms are stamped to communicate this state to the study team. Details of data
7 management are included in a separate data management SOP.

8
9 Data will be entered in a MS ACCESS with filters for invalid entries and missing
10 values by project personnel at the data unit and time and date stamping. Complete
11 double data entry with verification will be performed. Validation of the DDE system
12 will be performed using STATA or a similar program. All inconsistencies will be
13 resolved by the data manager in communication with the Study Coordinator or
14 project PI. These files will be saved and available for review as part of the audit
15 trail to document data integrity.

1

2

3 **15.3 Timing/Reports**

4

5 The report content and timing is specified in the DSMP.

6

7 **15.4 Study Records Retention**

8

9 Study documents will be retained for a minimum of 7 years after the data is accrued in
10 accordance with regulations regarding the conduct of clinical trials in Peru. They will be
11 secured in locked furniture in the AB PRISMA offices in Iquitos.

1

2

3 **15.5 Protocol Deviations**

4

5 A protocol deviation is the con-compliance with the specified clinical trial protocol, GCP,
6 MOP, or laboratory SOP procedures. The non-compliance can be the result of logistics,
7 the investigator, study site staff, or the subject. It is however, always the responsibility of
8 the site PI to identify protocol deviations, characterize the nature, extent, and reason for
9 the deviation, and report them as appropriate to the INS, the IRBs of AB PRISMA,
10 Tulane, Johns Hopkins University, and the sponsor in a timely manner.

11

12

13 Protocol deviations are recorded on a form and become part of the study file reported to
14 the IRB annually if the deviation is characterized as one warranting reporting. All protocol
15 deviations should be included in the reports to the DSMB as well.

16

17

18 Study deviations that are recorded that are purely the result of study compliance (such as
19 missing stool specimens, or specimens collected 3 days late) are reviewed by the study
20 staff but not reported to IRBs.

1

2

3 **16 STUDY ADMINISTRATION**

4 **16.1 STUDY LEADERSHIP AND GOVERNANCE**

5

6 **16.1.1 Steering Committee**

7

8 The Steering Committee will govern the conduct of the study. The Steering Committee
9 will be composed of the study PI and co-PI and representatives of the sponsoring NIH
10 Institute (NIDDK), the study coordinator (AB PRIMSA), the local PI ([name]
11 [name]) and the PI of the laboratory of AB Prisma in Iquitos. The Steering Committee
12 will oversee protocol and MOP development and meet by phone once prior to study
13 initiation for final review of study materials. The steering committee members will receive
14 the reports of the medical monitor and meet by teleconference on an ad hoc basis.

15

16 **16.1.2 Executive Committee**

17

18 An executive committee is not required to coordinate and oversee a small single site study
19 that already has DSMB oversight

20 .

21 **16.1.3 Conflict of Interest Policy**

22

23 The study product is supplied free of charge by BioGaia, (or with a minimal charge to
24 cover product labelling and shipping). BioGaia does not participate in study design,
25 data analysis, or sponsor this trial with additional funds. No member of the
26 investigative staff owns stock in or receives any compensation from BioGaia, nor have
27 they in the past. BioGaia makes no determinations regarding the study outcomes, nor
28 do they have any capacity to influence data analysis or the dissemination of results.

1

2

3 **16.2 SUBCOMMITTEES**

4

5 No subcommittees are planned for this small single site study. Prior to enrollment the
6 trial will be registered at clinicaltrials.gov. All resulting publications will be submitted to
7 the digital archive at Pubmed Central as per NIH public access regulations
8 (https://grants.nih.gov/grants/NIH-Public_Access-Plan.pdf) and preferentially submitted
9 to journals that have open access options.

10

11

APPENDIX A: STUDY PROCEDURES

Version 18 MAR 2015

Appendix A. Study schedule for participants 0 to 2 years of age. Blood collection at 5 and 28 days can have a 48 hour window to allow for difficulty in scheduling visits. Stool collection has an inherent challenge in collecting samples on time. A 48 hr window will be allowed, after which the sample will be counted as missing. The scheduling of visits at 36 and 90 days will have a one week window, after which a protocol deviation form must accompany the safety information collected at these time points (data will be sought and recorded even beyond the scheduled window).

Procedure	PRE-RX DAY 0	DAY 1	DAY 2	DAY 3	DAY 4	DAY 5	DAY 8	DAY 12	DAY 15	DAY 18	DAY 24	DAY 28	DAY 36	DAY 90
Informed Consent	X													
Medical History	X													
Physical Examination	X													
Record Temperature	X	X	X	X	X	X	X	X	X	X	X	X		
Concomitant Medications	X	X	X	X	X	X	X	X	X	X	X	X		
Stool Sample	X			X		X		X	X	X	X	X	X	
Blood Chemistry	X					X						X		
Hematology	X					X						X		
Assign Treatment Number	X													
Dispense Diary Cards		X												
Receive Study Product		X	X	X	X	X								
Maintain Diary		X	X	X	X	X	X	X	X	X	X	X		
Collect Adverse Events		X	X	X	X	X	X	X	X	X	X	X		x
Collect Diary Cards												X		

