Subjects with fever will be referred to the study physician for a full physical exam and collection of specimens for fever evaluation (malaria smear, blood culture). Subjects with serum hemoglobin less than 11 gm/dL at baseline or at day 5 (or Hb less than 9.5 gm/dl at baseline or at day 5 for infants 5 months of age or younger) will be treated with iron supplementation in the form of iron sulfate drops or chewable iron tablets, according to American Academy of Pediatrics guidelines [Clinical Report—Diagnosis and Prevention of Iron Deficiency and Iron-Deficiency Anemia in Infants and Young Children (0–3 Years of Age) Baker RD, Greer FR, The AAP committee on Nutrition; Pediatr 126 (5): 1-11, 2010] (PMID:20923825). When indicated, iron supplementation will be provided starting at least 5 days after the last dose of study product to prevent confounding the assessment of study related adverse events with the common side effects of supplemental iron therapy (gastrointestinal upset, etc), an administration of iron supplementation will be controlled for in analysis of adverse event data (clinical and laboratory test outcomes by study group at days 5 and 28). Treatment will consist of an oral liquid formulation dosed at 3-6 mg elemental iron/kg/24 hours. Iron supplementation will be continued for 2 months after initiation, and serum hemoglobin will be measured using blood collected by fingerstick tested in a HemoCue device at the end of the 2 months treatment period. Children with serum hemoglobin less than 11 gm/dL at this 2 month point (or less than 9.5 gm/dl at baseline or at day 5 for infants 5 months of age or younger) will be referred to a local pediatrician for further evaluation and individualized treatment if needed. Individuals with helminth infection will be treated with albendazole therapy based on cumulative testing results on study day 36. For ascaris and hookworm this consists of one dose of albendazole, whereas doses will be given for 3 days for trichuris and strongyloides infections.

Stool samples will be obtained on day 3, 5, 12, 15, 18, 24, 28, and 36 for the presence of *Lactobacillus reuteri* by PCR.

B. Day 28 to 3 month endpoint. After day 28, parents of the subjects will be instructed to report all episodes of febrile illness occurring during the 3 month follow-up period, and to present to the study clinic for fever evaluation whenever the parents of the subject

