16 treatment group. The normal range for each parameter will be used to create categories
17 of low, normal, or high. Any result higher than the upper limit normal (ULN) will be
18 categorized as high, any result lower than the lower limit of normal (LLN) will be
19 categorized as low, and any result within the LLN and ULN will be categorized as normal.
20 The number and percentage of subjects in each shift category from baseline to final
21 evaluation will be shown for each parameter. Only the hematology and blood chemistry
22 tests with a numeric normal range and at least one follow-up value will be analyzed for
23 shifts from baseline. The number and percentage of subjects with clinically significant
24 values will be presented.

25
26 **B. The secondary outcome measurements** are

27
28 1. To determine the duration of shedding of *L. reuteri* DSM 17938 following controlled
29 administration.

30
31 Since the longitudinal nature of the repeated PCR assays results in correlated outcomes,
32 generalized estimating equations (GEE) will be used to model the binary response
33 whether subjects exhibited a positive PCR result during the various period of study. The
34 duration of shedding of *L. reuteri* will be assessed using Kaplan Meier Product limit
35 estimates.

36
37
38
39
40 **11.2 Sample Size Considerations**

1
2
3 The sample size for this Phase 1 safety trial in healthy children aged 2-24 months is
4 determined by historical precedent for safety in human use.

5
6 Enrollment for the prior Phase 1 studies in adults (Safety of LR in Healthy volunteers
7 #NCT00774163) and children (Safety of LR in healthy children 2 to 5 years of age in Peru
8 #NCT02124122) have been able to recruit and retain >95 subject (Phase 1 child study in
9 progress). We have high and similar rates of retention in our other studies with more
10 complexity and participant burden, even among our birth cohorts.³⁷

11
12 Missing data will not be imputed. Data will be analyzed per treatment group assignment
13 after the administration of a single dose of product for all safety and tolerability analyses.
14 Data regarding the duration of carriage will be restricted to those individuals who complete
15 5 days of therapy.

16
17 The amount of subjects in this study will likely be underpowered to detect differences in
18 most secondary outcomes. This is in part due to the lack of information on key

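### Stools more than 48 hours late count as missing, yet the day-36 visit, for which the schedule table lists only a stool, has a one-week window

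*Combined protocol and SAP*

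**What the plan says.** The note above the schedule table in Appendix A concedes that stools will not always be on time: "Stool collection has an inherent challenge in collecting samples on time". It then sets the stool rule: "A 48 hr window will be allowed, after which the sample will be counted as missing". The following sentence sets a different allowance for two visits: "The scheduling of visits at 36 and 90 days will have a one week window". After that week a deviation form must accompany the safety information, but "data will be sought and recorded even beyond the scheduled window".

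In the table itself, the day-36 column has one mark, for the stool sample. Temperature, concomitant medications and the diary end at day 28. Adverse-event collection skips day 36 and resumes at day 90.

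Section 7.5 repeats the stool schedule: "Stool samples will be obtained on day 3, 5, 12, 15, 18, 24, 28, and 36 for the presence of" *L. reuteri* by PCR. Under Section 3.2.2 the duration of shedding is the only secondary outcome. Section 11.1 models the repeated PCR results by GEE and says that duration "will be assessed using Kaplan Meier Product limit" estimates. Section 11.2 adds: "Missing data will not be imputed". Section 15.5 gives, as examples of compliance deviations reviewed by study staff, "missing stool specimens, or specimens collected 3 days late".

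**The concern.** Two allowances meet at day 36 and do not line up. A child seen four days late is within the visit window, with no deviation to record, yet the one sample tabulated for that visit is treated as if it had never been taken. Section 15.5 names missing stools and late stools as separate things; the Appendix A rule turns the second into the first.

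Day 36 is the worst place for this. It is the last stool, so no later sample can make up for it, and it follows the longest gap in the schedule. For a time-to-event outcome, a PCR result with a known collection date says something about shedding on that date even when it is late. For a child positive at day 28, a negative stool on day 40 places clearance between those days, and a positive one extends follow-up to day 40. Under the current rule both children are censored at day 28.

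A related gap is that neither Section 11.1 nor Appendix A says whether a stool is analysed at its actual or its scheduled day.

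**Working it through.** The plan gives no figure for late stools, so there is none to reproduce. The check is a day count followed by a range under stated assumptions.

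**Inputs from the documents**
- Post-dose stools: days 3, 5, 12, 15, 18, 24, 28 and 36, which is 8 per child (Sections 3.2.2 and 7.5). The gaps are 2, 7, 3, 3, 6, 4 and 8 days, so the last gap, 36 − 28 = 8 days, is the longest.
- 60 children randomised 2:1 (Section 4): 60 × 2/3 = 40 active and 20 placebo.
- Planned post-dose stools: 60 × 8 = 480.
- Stool window 48 hours; day-36 visit window one week (Appendix A).

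**Day count, lateness only**
- Visit in window: days 36 to 43, which is 8 days.
- Stool counted: days 36 to 38, which is 3 days.
- Visit in window but stool counted as missing: days 39 to 43, which is 8 − 3 = 5 of the 8 permitted days.

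The 5 of 8 is a share of permitted days, not a forecast of visits. The stool rule is worded for lateness and does not address early samples.

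**Assumptions (not in the documents)**
- Share of day-36 stools taken on days 39 to 43: 5% to 30%.
- Share of active children still PCR-positive at day 28: 10% to 50%.
- The Kaplan-Meier event is first clearance. Section 11.1 does not define it.
- All 40 active children are in the analysis. Section 11.2 restricts it to those completing five days of therapy, so 40 is an upper limit.

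**Stools lost at day 36**
- Low: 0.05 × 60 = 3, and 3/480 = 0.6%.
- High: 0.30 × 60 = 18, and 18/480 = 3.75%, or about 4%.
- In the active arm: 0.05 × 40 = 2 to 0.30 × 40 = 12.

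**Active children losing Kaplan-Meier follow-up after day 28** = 40 × share late × share positive at day 28

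| Share late | 10% positive | 30% positive | 50% positive |
|---|---|---|---|
| 5% | 0.2 | 0.6 | 1.0 |
| 10% | 0.4 | 1.2 | 2.0 |
| 20% | 0.8 | 2.4 | 4.0 |
| 30% | 1.2 | 3.6 | 6.0 |

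**The case against.** The strongest reply is that the two windows govern different things. One is a rule for specimens. The other concerns visit scheduling, and its deviation clause refers to safety information. An on-time visit with a missing specimen is awkward but can be carried out. That stands: a reader might infer that the two sentences contradict each other, and strictly they do not.

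Day 36 also has other uses. Section 7.5 ends intense monitoring then, has symptoms recorded for six weeks, and ties helminth treatment to cumulative results on that day. So the stool is the only procedure in the Appendix A table, not the only mention of day 36 in the protocol. This gives the one-week window a possible purpose, but it does not save the stool.

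A tight window is defensible in mid-schedule, where days 12, 15 and 18 are three days apart and a 48-hour limit keeps samples with their visits. Nor is a late result fully informative. Section 11.2 says that about 10% in this age range test positive and that the frequency of intermittent positive stools is unknown, so a late positive need not be persistence of the product strain. That limits what a late stool can show; it does not justify dropping it.

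Two stronger readings are tempting. One is that in-window stools are analysed at their scheduled day and so misdated by up to two days. The plan does not say so; it is silent. The other is that every late active child, 2 to 12 of 40 under the assumptions above, loses follow-up. With first clearance as the event, a child who cleared by day 28 has already had it. Finally, Section 5.4.4 expects missed visits and procedures to be low, which points to the lower end of the range.

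**Conclusion.** The concern holds in a limited form. The stated rule discards dated PCR results from visits that are themselves in window, at the last shedding time point and after the longest gap. With no imputation, a child still positive at day 28 and sampled on days 39 to 43 contributes nothing after day 28.

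The size is probably small: about 0.2 to 6 of 40 active children lose Kaplan-Meier follow-up, and at most about 4% of planned post-dose stools are lost. Both figures rest on the assumed late and positive shares, which the documents do not supply; the first also takes the event as first clearance. The mismatch between windows is confined to day 36, and no primary safety or tolerability outcome is affected. Section 11.2 already expects too little power for most secondary outcomes but wants these data to inform the phase 2 trial, which is reason enough to keep samples already in hand. This is a minor improvement.

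**What to change.** In Appendix A, give the day-36 stool the same one-week window as its visit, and replace the counted-as-missing clause so that 48 hours is the deviation trigger for the other stools. Section 15.5 already provides for such deviations.

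In Section 11.1, state that every stool with a recorded collection date is tested and analysed at its actual collection day, both in the Kaplan-Meier analysis and as the time variable in the GEE. Name one time origin. This is needed because Section 6.5 lets dosing run over six days with follow-up unchanged, and because the day of the first dose is day 0 in Section 7.5 but day 1 in Appendix A. Define the Kaplan-Meier event in the same place. Add a sensitivity analysis restricted to stools collected within their windows.

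Do not reassign stools to the nearest scheduled day. A day-12 stool taken on day 14, valid under the present rule, is two days from day 12 and one from day 15, so it would move to day 15 and could collide with that child's own day-15 stool.

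The cost is a few sentences of text, a few extra PCRs on stools already collected, and uneven visit times in the GEE. No extra visits are needed.
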